4.2.3 Primary Endpoint: Complete Response Rate (CRR)

The primary efficacy endpoint for Part B Dose Expansion (B2) is CRR assessed by BICR based on modified Lugano criteria for lymphoma.

CRR is a secondary endpoint for Part A Dose Escalation assessed by Investigator based on modified Lugano criteria and RECIL criteria.

4.2.3.1 Definition and Derivations

CRR is defined as the percentage of participants with CR, with the denominator defined as the number of participants in the response-evaluable analysis set.

Data obtained until progression, or last evaluable assessment in the absence of progression, will be included in the assessment of CRR, regardless of whether the participant withdraws from therapy. Participants who discontinue treatment without a response, receive subsequent anti-lymphoma therapy and then respond will not be included as responders in the CRR.

The CRR will include data of all scans, regardless of whether it was scheduled or not.

CRR as a secondary endpoint for Part A will be defined similarly but taking Investigator responses and based on modified Lugano criteria and RECIL criteria. Data will be recorded in the eCRF.

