#### Participants discontinuing study treatment while in response (PR/CR) or with SD:

Participants will enter the safety follow-up and will carry on with efficacy assessments by imaging until PD, start of a new anti-cHL therapy or EoS, whichever comes first (Table 4 and Table 16).

Note:

- Radiotherapy administered alone after the last dose of sabestomig while a participant is in CR, with a consolidation intent will not be considered as a new anti-cHL line of therapy. Therefore, the participant should carry on the efficacy follow-up and perform disease assessment by imaging as per SoA (Table 16).
- Participant in CR/PR who proceeds to HSCT without any treatment between the last dose of sabestomig and the start of the conditioning regimen will be followed-up for disease assessment post-transplant as per SoC and data on their disease status will be collected in the EDC as part of the survival follow-up.

See the SoA (Table 1, Table 2, Table 3, and Table 4) for data to be collected at the time of discontinuation of study intervention and follow-up and for any further evaluations that need to be completed.

If the participant does not agree to continue in-person study visits, a modified follow-up must be arranged to ensure the collection of endpoints and safety information. This could be a telephone contact with the participant, a contact with a relative or treating physician, or information from medical records. The approach taken should be recorded in the medical records. A participant who agrees to modified follow-up is not considered to have withdrawn consent or to have withdrawn from the study.

All participants in Safety or Survival follow-up at the time of final study DCO will be contacted by the study site prior to the final study DCO to confirm their survival status and to inform participants that this was the last study-related contact, and no further survival data will be collected in respect to the study. Sites are requested to document this last contact in the source records.

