4.2.2.1 Definition and Derivations

Objective Response (OR) is defined as a Best Overall Response (BOR) of CR or PR that occurs prior to the initiation of subsequent anticancer treatment and prior to progression. Objective Response Rate (ORR) is defined as the percentage of participants with objective response.

Data obtained from first dose until progression, or last evaluable assessment in the absence of progression, will be included in the assessment of ORR, regardless of whether the participant withdraws from therapy. Participants who discontinue treatment without a response, receive subsequent anti-lymphoma therapy and then respond will not be included as responders in the ORR (ie, the visit contributing to a response must be prior to subsequent therapy for the participant to be considered as a responder).

The ORR will be based on the BICR assessment, using modified Lugano criteria for lymphoma including data of all scans for Part B, regardless of whether it was scheduled or not.

ORR for Part A will be defined similarly but taking Investigator responses and based on modified Lugano criteria and RECIL criteria. Data will be recorded in the eCRF.

Best overall response

Best Overall Response (BoR) will be determined using disease assessments at different evaluation time points from the date of the first dose of study treatment until documented disease progression or start of any further anti-cancer therapy, whichever is earlier. Clinical deterioration will not be considered as documented disease progression. Categories of BOR will be based on modified Lugano criteria using the following response criteria: CR, PR, stable disease [SD], progressive disease [PD], and not evaluable [NE], and RECIL criteria using the following criteria: CR, PR, minor response [MR], SD, PD, and NE.

BoR will be calculated based on Investigator assessed data for part A efficacy analysis based on RECIL criteria, and based on BICR assessed data for part B analysis. The images of the participants dosed at RP2D in part A will undergo a retrospective assessment by BICR whose result will be combined with other BICR-based part B data for Part B analysis.

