Initiation of subsequent anticancer, excluding BM transplantation treatment prior to PD or death	Date of last evaluable disease assessment prior to initiation of subsequent anticancer treatment	Censored

Abbreviations: BM bone marrow, PD, progressive disease; PFS, progression-free survival

If response is defined as CR or PR, provided the participant did not receive any new anti-cancer treatment for Hodgkin lymphoma from the last dose of sabestomig and start of the preconditioning for the BM transplantation. If the participant received any new treatment (before the BM transplantation), he would follow the censoring rules for new treatment for Hodgkin lymphoma. The information will be collected in the EDC.

Radiotherapy consolidation for a participant in complete response is not considered a subsequent anticancer treatment.

The PFS time is always derived based on scan/assessment dates, not visit dates. Disease assessments/scans contributing towards a particular visit may be performed on different dates. The following rules are applied:

 The date of progression is determined based on the earliest of the dates of the component that triggered the progression.

Note: for target lesions only the latest scan date is recorded out of all scans performed at that assessment for the target lesions and similarly for non-target lesions only the latest scan date is recorded out of all scans performed at that assessment for the non-target lesions.

Duration of follow-up for PFS is applicable only for PFS censored participants and is defined as follows:

Duration of follow-up for PFS in censored participants (months) = (date of PFS event [progression/death] or censoring – date of first dose + 1) / (365.25/12).

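### The CRR rule does not require the complete response to precede subsequent therapy, so a PR that becomes a CR after transplant is not clearly excluded from Cohort B2's primary endpoint

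*SAP*

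**What the plan says.** SAP 4.2.3 sets the endpoint: "The primary efficacy endpoint for Part B Dose Expansion (B2) is CRR assessed by BICR based on modified Lugano criteria for lymphoma". SAP 4.2.3.1 then gives four rules.

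- Rate: "CRR is defined as the percentage of participants with CR, with the denominator defined as the number of participants in the response-evaluable analysis set".
- Data window: "Data obtained until progression, or last evaluable assessment in the absence of progression, will be included in the assessment of CRR". Withdrawal from therapy does not close it.
- Scans: "The CRR will include data of all scans, regardless of whether it was scheduled or not".
- Exclusion: "Participants who discontinue treatment without a response, receive subsequent anti-lymphoma therapy and then respond will not be included as responders in the CRR". Protocol 9.4.2.1 uses the same sentence.

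The SAP treats ORR more strictly. SAP 4.2.2.1 defines objective response as a best overall response (BOR) of CR or PR "that occurs prior to the initiation of subsequent anticancer treatment and prior to progression". It adds that the visit showing the response has to come before subsequent therapy. The BOR window itself closes at progression or at further anti-cancer therapy. SAP 4.2.3.1 mentions neither BOR nor either timing condition.

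On transplant, protocol 7.1 says that a participant in CR or PR who goes straight from sabestomig to HSCT "will be followed-up for disease assessment post-transplant as per SoC", with disease status entered during survival follow-up. The PFS censoring table (SAP 4.2.6.2, Table 4) words its new-therapy row as "Initiation of subsequent anticancer, excluding BM transplantation treatment prior to PD or death". A footnote limits that exception to transplant in CR or PR with no new anti-cancer treatment between the last dose and preconditioning.

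**The concern.** The exclusion sentence has the same form for ORR and CRR, but it works only for ORR. A participant in PR is already an ORR responder, so a later CR changes nothing. For CRR the same participant is a non-responder, and a later CR moves them into the numerator. Such a participant did not stop treatment *without a response*, because the SAP's own objective response includes PR. The extra protection in the SAP sits on the endpoint that needs it less.

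At stake are B2's primary rate, its exact 95% interval (SAP 4.2.3.2) and the final No-Go assessment on CRR (protocol 9.5.2). The supportive Investigator-assessed CRR (SAP 4.2.3.4) rests on the same definition and has no central-review filter. Any error goes one way, towards a higher CRR.

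**Working it through.** There is no plan figure to reproduce. B2's sample size, target value and operating characteristics are redacted, and none is stated to depend on this rule. The check is therefore a reading of the rules, followed by an illustration of size.

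**1. Literal outcome by path**

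| Path | ORR (SAP 4.2.2.1) | CRR (SAP 4.2.3.1) |
|---|---|---|
| No response, new therapy, then CR | Not a responder | Excluded by the sentence |
| PR, other new therapy, then CR | Responder, on the PR | Not excluded |
| PR, straight to HSCT, then CR | Responder, on the PR | Not excluded |
| CR, then consolidation radiotherapy | Responder | Already a complete responder |

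Consolidation radiotherapy is not an extra route, because its exemption applies only to participants already in CR.

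**2. Other new therapy.** Protocol 8.1 ends efficacy assessments at the start of new cHL treatment, so a later CR should rarely be observed. Counting one would also contradict the duration of complete response (DoCR) in SAP 4.2.5.2:

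DoCR = (PFS event or censoring date − first CR date + 1) / (365.25/12)

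Table 4 censors PFS at the last evaluable assessment before the new therapy. With illustrative days, censoring on day 120 and a CR on day 200, DoCR = (120 − 200 + 1)/30.4375 = −79/30.4375 = −2.6 months. This route is largely closed.

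**3. Transplant in PR, no intervening therapy.** PFS is not censored at this transplant, so DoCR would be positive and nothing downstream would flag the CR. Whether central review would see it is not settled. Protocol Table 4 collects post-HSCT status by telephone, email or clinic visit in survival follow-up. Protocol 8.1.3 sends unscheduled assessments to central review, and the CRR rule admits unscheduled scans. No section says whether standard-of-care scans after transplant are among them.

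**4. Size.** Each conversion adds 1/N. The assumed N of 40 is obtained as follows:

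- 180 (protocol 9.2) − 52 in Part A (SAP 3.3.7) = 128 in Part B.
- A B1 total of 100 (protocol 9.2) − an assumed 12 treated at the RP2D in Part A = 88 new in B1.
- 128 − 88 = 40.

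The 100 may not have been read reliably from the PDF, so a range is needed: 1/20 = 5.0 points, 1/40 = 2.5 points, 1/60 = 1.7 points.

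With N = 40 and an assumed 12 CRs before any further therapy (exact 95% intervals):

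| Conversions counted | CRR | 95% CI |
|---|---|---|
| 0 | 12/40 = 30.0% | 16.6 to 46.5 |
| 1 | 13/40 = 32.5% | 18.6 to 49.1 |
| 2 | 14/40 = 35.0% | 20.6 to 51.7 |
| 4 | 16/40 = 40.0% | 24.9 to 56.7 |

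**5. No-Go.** B2's target value and probability threshold are both redacted. Taking the Beta(1,1) prior, N = 40 and the 10% threshold shown for B1 (protocol Table 22), the fewest CRs that avoid No-Go are 9, 12 and 16 for assumed target values of 30%, 40% and 50%. One conversion would change the result only if the count without it were exactly 8, 11 or 15 respectively.

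**The case against.** The strongest case on the other side is that the documents never tell anyone to count these CRs.

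- In a CRR paragraph, *without a response* may mean without a CR. SAP 4.2.5.2 uses response in that sense when it dates the initial response for DoCR. If CRR were derived from BOR, the BOR window would exclude the cases. This stands as a possible reading. However, SAP 4.2.3.1 does not refer to BOR, and SAP 4.2.5.2 also limits DoCR to participants with objective response, so usage is not uniform.
- A status taken by telephone is not a central Lugano read. Protocol 7.1 also contrasts consolidation radiotherapy, where scheduled imaging continues, with HSCT, which moves to standard-of-care follow-up. This stands, and it makes the transplant route into the primary endpoint uncertain.
- The PFS rules do not govern CRR, and SAP 4.2.6.1 names transplant in response alongside subsequent anticancer treatment. That is correct. It shows that the SAP has no settled convention on transplant that could be carried over to CRR.
- No formal hypothesis is tested (protocol 9.1), protocol 9.5 names Investigator ORR as the interim efficacy endpoint, and stopping recruitment is at the sponsor's discretion. This lowers the stakes but leaves the primary estimate exposed.

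A reader might infer that the plan credits sabestomig with CRs produced by conditioning and transplant, or that B2's CRR will be inflated by several points. The documents support neither. The first is one reading of an incomplete rule. The second needs PR, transplant and conversion rates that appear nowhere in the documents.

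**Conclusion.** The concern holds as a gap in the definition of a primary endpoint. Read literally, a PR that becomes a CR after further therapy is not excluded from CRR and could count, both in B2's primary endpoint and in the supportive Investigator CRR. The gap is practically confined to HSCT in PR with no intervening therapy. For the primary endpoint it further depends on whether post-transplant scans reach central review, which the documents leave open.

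The size cannot be established. The per-conversion figure is simple arithmetic on an assumed N, and the number of conversions is unknown. The effect on No-Go cannot be stated without B2's target value and threshold.

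**What to change.** In SAP 4.2.3.1 and protocol 9.4.2.1:

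- Define complete response as a BOR of CR occurring before progression and before any subsequent anti-lymphoma therapy, matching the SAP's ORR definition.
- In the exclusion sentence, change *without a response* to *without a complete response*.
- State that, for CRR, HSCT including its conditioning ends the response window. The PFS transplant rule can stay as it is.

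The wording should be settled before database lock. Deciding after seeing who was transplanted would be a post hoc choice on a primary endpoint. The cost is about two sentences in each document, and CRR may be slightly lower. The change also removes the negative durations shown above.

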4.2.3.2 Primary Analysis of Primary Endpoint: CRR

CRR will be calculated and binomial exact two-sided CIs at 95% will be presented for participants in the response-evaluable analysis set.

4.2.3.3 Sensitivity Analysis of Primary Endpoint: CRR

As sensitivity analysis, if the number of participants in FAS is different from that in Response Evaluable Set, a summary of will be used in this analysis. For the computation of CRR, participants with will be included in the FAS and will be considered non-responders.

4.2.3.4 Supportive Analysis of CRR Endpoint

A supportive analysis of CRR for Part B will be performed using Investigator responses and based on modified Lugano criteria and RECIL. Data will be recorded in eCRF.

4.2.3.5 Subgroup Analyses

The following subgroup analysis may be performed for CRR (primary efficacy variable):

 Participants who are brentuximab naïve versus participants who are brentuximab exposed.

4.2.4 Secondary Endpoint: Duration of Response (DoR)

DoR is a secondary endpoint for Part A Dose Escalation and Part B Dose Expansion. Responses assessed by Investigator for Part A using modified Lugano and RECIL criteria and by BICR for Part B using modified Lugano.

4.2.4.1 Definition

DoR is defined as the time from the date of first documented objective response (CR or PR) until date of first documented disease progression or death (by any cause in the absence of disease progression).

4.2.4.2 Derivations

DoR (months) = (date of progression free survival [PFS] event [progression/death] or censoring – date of first objective response + 1) / (365.25/12).

The end of response should coincide with the date of progression or death from any cause used for the PFS endpoint. The time of the initial response is defined as the latest of the dates contributing towards the first visit response of CR or PR. If a participant does not progress following a response, then their DoR is censored on the PFS censoring date. Only participants who have achieved objective response are evaluated for DoR.

4.2.4.3 Analysis of Secondary Endpoint: DoR

The analysis of DoR will include all participants in the response-evaluable analysis set. Only participants who achieved objective response (CR or PR) will be included in the summaries of DoR. Kaplan-Meier plots of DoR with at least responders per dose level may be presented. The median DoR and 2 sided 95% CI will be estimated using the Kaplan-Meier method. In addition, percentage of participants remaining in response at 3, 6, 12, 18 and 24 months after initial response may also be presented. These time points may be adjusted according to actual data observed in the study without amendment to this SAP. Reasons for censoring for DoR will also be summarized.

Swimmer plots by participant (including non-responders) with symbols to display each participant's study status will be presented.

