Efficacy	• To assess the preliminary antitumor activity of sabestomig in participants with r/r cHL	
 
Complete Response Rate, Objective Response Rate, DoR, and DoCR, and PFS including landmarks at 12 and 24 months a
 
OS including landmarks at 12 and 24 months
 
		
Part B Dose Expansi	on			
Efficacy	• To further assess the preliminary antitumor activity of sabestomig in participants with r/r cHL	
 
DoR, DoCR, and PFS including landmarks at 12 and 24 monthsb
 
OS including landmarks at 12 and 24 months
 
		
Patient-Reported Outcomes	• To assess patient-reported treatment-related symptoms, overall side-effect bother, and overall global health status while on sabestomig	
 
Proportion of participants reporting different levels of presence/magnitude/interference (as applicable) of diarrhea, rash, and fatigue over time based on PRO-CTCAE or Peds-PRO-CTCAE.
 
Proportion of participants reporting different levels of overall side-effect bother over time based on the PGI-TT.
 
Proportion of participants reporting different levels of quality of life/health over time based on the EORTC ILXX QL2 items.
 
		
Part A Dose Escalation and Part B Dose Expansion				
РК	• To assess the PK of sabestomig in participants with r/r cHL	• PK parameters including the maximum observed concentration, area under the concentration-time curve, clearance, and terminal elimination half-life		
Immunogenicity	• To assess the immunogenicity of sabestomig in participants with r/r cHL	Incidence of anti-drug antibodies against sabestomig in serum		

Table 6	Secondary	Objectives	and Endpoints
	Secondary	Objectives	and Endpoints

a Disease response will be assessed according to Investigator assessment using Modified Lugano (2014) (Cheson et al, 2014) and RECIL criteria (Younes et al, 2017).

b Disease response will be assessed according to Blinded Independent Central Review using Modified Lugano (2014) (Cheson et al, 2014).

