# 9.4.2.2 Secondary Endpoint(s) Duration of Response

The DoR is defined as the time from the date of first documented response, assessed by Investigator for Part A and by BICR for Cohorts B1 and B2, using the Modified Lugano criteria, until the date of documented progression or death due to any cause (in the absence of disease progression). The end of response should coincide with date of progression or death from any cause used for the PFS endpoint. The time of the initial response will be defined as the latest of the dates contributing towards the first visit that was CR or PR.

The analysis will include all participants in the response-evaluable analysis set who had a response, regardless of whether the participant withdraws from therapy.

If a participant does not progress following a response, then the DoR will use the PFS censoring time.

Kaplan-Meier plots of DoR will be presented if data permitted. Median DoR, including 95% CIs, will also be presented, calculated from the Kaplan-Meier curve. In addition, the number of participants still responding at 3, 6, and 12 months after initial response will also be presented. Swimmer plots that clearly show the profile of each participant who responds will also be produced.

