#### **Duration of Complete Response**

The DoCR is defined as the time from first documented CR, assessed by the Investigator for Part A and by BICR for Cohorts B1 and B2, using Modified Lugano criteria, until the date of documented relapse/progression or death due to any cause (in the absence of disease progression).

The analysis will include all participants in the response-evaluable analysis set who had a response, regardless of whether the participant withdraws from therapy.

If a participant does not progress following a response of CR, then the DoCR will use the PFS censoring time.

Kaplan-Meier plots of DoCR will be presented if data permitted. Median DoCR, including 95% CIs, will also be presented, calculated from the Kaplan-Meier curve. In addition, the number of participants still responding at 3, 6, and 12 months after initial response will also be presented. Swimmer plots that clearly show the profile of each participant who responds will also be produced.

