4.2.6.3 Analysis of Secondary Endpoint: PFS

The main analysis of PFS is based on the FAS. The number and percentage of participants experiencing a PFS event (broken down by type of event/censoring) and Kaplan-Meier plots of PFS, for dose levels with at least participants may be presented. The median PFS and its two-sided 95% CI will be estimated using the Kaplan-Meier method (if participant numbers allow).

The intervention status at progression of participants at the time of analysis will be summarized. This includes the number (%) of participants who were on intervention at the time of progression, the number (%) of participants who discontinued study intervention prior to progression, the number (%) of participants who have not progressed and were on intervention or discontinued intervention.

A summary of the duration of follow-up for PFS is included using median (range). This will be presented for censored participants (including all types of PFS censoring).

The proportion of participants alive and progression free at 3, 6, 12, 18 and 24 months and associated two-sided 95% CI will be estimated using the Kaplan-Meier method. Other landmark rates may be considered per sponsor discretion.

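### The SAP makes the DoR and DoCR landmark times optional and movable on the observed data, although the protocol commits to 3, 6 and 12 months

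*SAP*

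**What the plan says.** SAP 4.2.4.3 fixes the main DoR summary: "The median DoR and 2 sided 95% CI will be estimated using the Kaplan-Meier method". For the landmarks it says that the "percentage of participants remaining in response at 3, 6, 12, 18 and 24 months after initial response may also be presented", and continues: "These time points may be adjusted according to actual data observed in the study without amendment to this SAP". SAP 4.2.5.3 carries the same two provisions for DoCR.

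The protocol is firmer. Under DoR, Section 9.4.2.2 says that "the number of participants still responding at 3, 6, and 12 months after initial response will also be presented". The DoCR paragraph makes the same commitment for the number "of participants still responding at 3, 6, and 12 months after initial response will also be presented". SAP Section 2, which is the place to declare departures from the protocol's analyses, declares none.

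PFS is worded differently. SAP 4.2.6.3 says: "The proportion of participants alive and progression free at 3, 6, 12, 18 and 24 months and associated two-sided 95% CI will be estimated", and then: "Other landmark rates may be considered per sponsor discretion". Protocol Table 6 gives the Part B secondary endpoints as "DoR, DoCR, and PFS including landmarks at 12 and 24 months".

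**The concern.** The clause is an express permission, not a gap. It names the observed data as the reason for moving a time point and sets no criterion for doing so, such as a minimum number at risk. Treatment is open label and there is no control group, so those who choose the landmarks can see the response data first.

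Durability matters to this programme. The synopsis gives the lack of durable response to anti-PD-1/PD-L1 monotherapy as part of the rationale. If a landmark is chosen because the curve looks good there, and less favourable months are left out, the reported durability rate will tend to be too high.

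**Working it through.** **1. The two documents side by side, for DoR and DoCR**

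| | Protocol 9.4.2.2 | SAP 4.2.4.3 and 4.2.5.3 |
|---|---|---|
| Months | 3, 6, 12 | 3, 6, 12, 18, 24 |
| Measure | number still responding | percentage still responding |
| Status | will be presented | may be presented |
| Can the months move? | no provision | yes, on observed data, without amendment |

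Adding 18 and 24 months does no harm. The conflict is that a protocol commitment has become optional and movable with no declared change.

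**2. What selection could do to a reported rate**

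The documents give no expected durability rate and no assumption for DoR, so there is no planned figure to reproduce. The size was examined by simulation, 4,000 runs per setting. All of these inputs are assumptions:

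- DoR exponential with median m = 6, 12 or 24 months, so the true rate is S(t) = 0.5^(t/m). For m = 12 this is 84.1%, 70.7%, 50.0%, 35.4% and 25.0% at the five listed months.
- 10, 20 or 40 responders.
- Censoring uniform over 12 to 36 months.

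In each run the error is e(t) = Kaplan-Meier estimate at t minus S(t). Past the last observation the curve was carried forward. For a fixed landmark the result is the mean of e(t). For a selected landmark it is the mean over runs of the largest e(t) among the months on offer.

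Fixed landmarks: mean error between -0.4 and +0.5 percentage points, except +1.3 in one sparse setting (24 months, 10 responders, median 6 months).

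Selected landmarks, in percentage points (range over the three medians):

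| Responders | Best of the five listed | 12-month landmark moved within 9 to 15 | Any half-month, 3 to 24 | For scale: SD of the fixed 12-month estimate |
|---|---|---|---|---|
| 10 | +10.9 to +12.0 | +6.8 to +8.1 | +13.7 to +15.7 | 13.7 to 15.8 |
| 20 | +7.5 to +8.3 | +4.8 to +5.9 | +9.8 to +11.2 | 9.5 to 11.0 |
| 40 | +5.4 to +5.9 | +3.6 to +4.2 | +7.2 to +8.1 | 7.0 to 7.8 |

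A separate run with 15 or 30 responders, medians of 9 or 15 months and censoring over 6 to 30 or 12 to 36 months gave +6.5 to +10.6 for the best of five and no bias at a fixed 12 months.

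**3. Is there an ordinary reason to move a landmark?**

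Protocol 9.4.1 allows a final analysis 6 months after the last participant starts. Assume uniform accrual over A months and response at month 2. Potential follow-up after response is then 6 - 2 = 4 months plus a uniform amount between 0 and A. The share of responders who could be followed to month L is (A - (L - 4))/A, with a floor of 0.

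- L = 12: 4/12 = 33% (A = 12), 10/18 = 56% (A = 18), 16/24 = 67% (A = 24).
- L = 18: 0%, 4/18 = 22%, 10/24 = 42%.
- L = 24: 0%, 0%, 4/24 = 17%.

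The later months may therefore be immature. SAP Sections 1 and 3.1 also tie the final cut-off to the last study visit or to the move to post-trial access, which could give longer follow-up.

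**The case against.** The strongest reply has four parts.

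- **Permission is not bias.** A Kaplan-Meier rate at a stated month is unbiased whichever months are printed. Bias needs selection on favourable results and suppression of the rest, and the SAP prescribes neither. The figures above also assume that the chooser knows the true curve, which no sponsor does. Since the curve only falls, choosing the highest rate just means choosing an early month, and the reader sees which month it is. This stands: the figures are upper bounds under assumed inputs.
- **Other output limits the damage.** The median and its confidence interval are not adjustable, reasons for censoring are summarised, DoR swimmer plots are planned, and efficacy results are listed. Protocol 9.4 also requires deviations from its plan to be reported in the CSR. A reader might infer that a moved landmark would be invisible in the report; these provisions do not support that. What remains is that a SAP which permits the move and declares no change makes it less likely to be recognised as a deviation.
- **Little depends on these rates.** No hypothesis is tested, and the No-Go and futility rules in protocol 9.5.1 and 9.5.2 use only ORR and CRR. This stands and limits the importance of the point.
- **Short follow-up is a fair reason for flexibility.** It is, for 18 and 24 months especially. But it calls for showing the number at risk or stating that the rate cannot be estimated, not for an open licence to move the month.

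**Conclusion.** The point holds for DoR and DoCR. The SAP turns committed protocol landmarks into optional ones that can be moved on the observed data, and declares no change. If time points are chosen on their results, the reported rate can be too high by roughly 5 to 12 percentage points at worst for the best of five landmarks with 10 to 40 responders. That range rests on exponential durations, the assumed medians and the assumed censoring. With fixed landmarks the bias is essentially nil.

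A reader might infer three stronger things that the documents do not support:

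- *The reported rates are biased upward.* The clause creates a risk; it does not establish a bias.
- *The PFS landmarks are open to the same selection.* The five listed PFS months must be estimated with confidence intervals, and the discretion in SAP 4.2.6.3 only adds to them.
- *Protocol Table 6 fixes 12 and 24 months for DoR and DoCR.* That phrase most naturally attaches to PFS. SAP Table 2 applies it to PFS and OS only, and protocol 9.4.2.2 gives 3, 6 and 12 months for the durations.

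The effect is confined to descriptive reporting of secondary endpoints. It should be corrected, but it does not threaten the primary analyses.

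**What to change.** Change the SAP wording as follows:

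- Delete the adjustment sentence in 4.2.4.3 and 4.2.5.3.
- State that DoR and DoCR will be presented at 3, 6 and 12 months, as in the protocol, with 18 and 24 months listed as additional descriptive times.
- Where follow-up is short, keep the landmark and print the number at risk or 'not estimable'.
- Label any other time point as post hoc, including extra PFS landmarks under 4.2.6.3. The listed PFS landmarks need no other change.

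The cost is an edit to the SAP. The one drawback is that some fixed landmarks may be reported as not estimable. Extra time points can still be shown if they are labelled.
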